	
sterilized male partner must use 2 methods of effective contraception. The investigator or a designated associate is requested to advise the patient on how to achieve an adequate birth control.
 
Adequate contraception is defined in the study as any medically recommended method (or combination of methods) as per standard of care.
 
12. Willingness and ability to comply with scheduled visits, treatment plan, laboratory tests and other study procedures.
 
13. Affiliation to the Social Security System.
 
Non-inclusion criteria
 
 
1. Previous or concurrent cancer that is distinct in primary site or histology from colorectal cancer within 5 years prior to study inclusion, except for curatively treated cervical cancer in situ, non-melanoma skin cancer and superficial bladder tumors [Ta (non invasive tumor), Tis (carcinoma in situ) and T1 (lamina propria invasion)].
 
2. Discovery of metastases within 6 months after the termination of adjuvant chemotherapy.
 
3. Previous treatment for metastatic disease. Radiotherapy within 28 days prior to first dose of treatment.
 
4. Active cardiac disease including any of the following: 
 
a. Congestive heart failure <math>\geq</math> New York Heart Association (NYHA) class 2,
 
b. Unstable angina (angina symptoms at rest), new-onset angina (begun within the last 3 months),
 
c. Myocardial infarction less than 6 months before first dose of treatment,
 
d. Cardiac arrhythmias requiring anti-arrhythmic therapy (beta blockers or digoxin are permitted).
 
 
 

--	-------------------------------------------------------------------------------------------------------------------------------------------------------------------------------------------------------------------------------------------------------------------------------------------------------------------------------------------------------------------------------------------------------------------------------------------------------------------------------------------------------------------------------------------------------------------------------------------------------------------------------------------------------------------------------------------------------------------------------------------------------------------------------------------------------------------------------------------------------------------------------------------------------------------------------------------------------------------------------------------------------------------------------------------------------------------------------------------------------------------------------------------------------------------------------------------------------------------------------------------------------------------------------------------------------------------------------------------------------------------------------------------------------------------------------------------------------------------------------------------------------------------------------------------------------------------------------------------------------------------------------------------------------------------------------------------------------------------------------------------------

	
 
5. ECG with a QT/QTc interval higher than 450 ms for men and higher than 470 ms for women Uncontrolled hypertension.
 
6. Uncontrolled hypertension. (Systolic blood pressure > 140 mmHg or diastolic pressure > 90 mmHg despite optimal medical management).
 
7. Arterial or venous thrombotic or embolic events such as cerebrovascular accident (including transient ischemic attacks), deep vein thrombosis or pulmonary embolism within 6 months before start of treatment.
 
8. Persistent proteinuria of National Cancer Institute Common Terminology Criteria for Adverse Events (NCI-CTCAE V5) grade 3 (i.e. urinary protein <math>\geq</math> 3.5 g/24 hrs)
 
9. Peripheral neuropathy > grade1 (NCI-CTCAE v5).
 
10. Major surgical procedure, open biopsy, or significant traumatic injury within 28 days prior to first dose of Treatment.
 
11. Ongoing infection > grade 2 (NCI-CTCAE v5).
 
12. Known history of human immunodeficiency virus (HIV) infection.
 
13. Chronic hepatitis B or C infection (if hepatitis status cannot be obtained from medical records, re-testing is required).
 
14. Seizure disorder requiring medication.
 
15. Symptomatic metastatic brain or meningeal tumors.
 
16. Evidence or history of any grade 3-4. Any hemorrhage or bleeding event <math>\geq</math> grade 3 (NCI-CTCAE v5) within 4 weeks prior to the start of study medication.
 
17. History of organ allograft.
 
18. Non-healing wound, ulcer, or bone fracture.
 
19. Dehydration Grade <math>\geq</math> 1 NCI-CTCAE v5).
 
20. Substance abuse, medical, psychological, or social conditions that may interfere with the patient's participation in the study or evaluation of the study results.
 
21. Known hypersensitivity to any of the study drugs, study drug classes, or any constituent of the products.
 
22. Interstitial lung disease with ongoing signs and symptoms.
 

--	-------------------------------------------------------------------------------------------------------------------------------------------------------------------------------------------------------------------------------------------------------------------------------------------------------------------------------------------------------------------------------------------------------------------------------------------------------------------------------------------------------------------------------------------------------------------------------------------------------------------------------------------------------------------------------------------------------------------------------------------------------------------------------------------------------------------------------------------------------------------------------------------------------------------------------------------------------------------------------------------------------------------------------------------------------------------------------------------------------------------------------------------------------------------------------------------------------------------------------------------------------------------------------------------------------------------------------------------------------------------------------------------------------------------------------------------------------------------------------------------------------------------------------------------------------------------------------------------------------------------------------------------------------------------------------------------------------------------------------------------------------------------------------------------------------------------------------------------------------------------------------------------------------------------------------------------------------------------------------------------------------------------------------------------------------------------------------------------------

	
23. Concomitant intake of St. John's wort.
 
24. Live attenuated vaccines are prohibited 10 days before the treatment, during the treatment and 3 months after the termination of treatment
 
25. History of gastrointestinal fistula or perforation
 
26. Inability to swallow oral medication.
 
27. Any malabsorption condition.
 
28. Pregnant or breast-feeding subjects.
 
29. Any condition that, in the opinion of the investigator, would interfere with the evaluation of study treatment or interpretation of patient safety or study results.
 
30. Participation in another clinical study with an investigational product during the last 30 days before inclusion.
 
31. Patients who might be interconnected with or dependent on the sponsor site or the investigator.
 
32. Legal incapacity or limited legal capacity.

STUDY PRODUCT OR MEDICAL DEVICE	FOLFIRINOX - REGORAFENIB
ENROLLMENT PROCEDURE	 
• Phase I part
 
The phase I part of this study will be designed as a standard 3+3 design for dose escalation/de-escalation and 3 to 6 patients will be enroled in each cohort sequentially, depending on occurrence of dose limiting toxicities.

TREATMENT MODALITIES	Pre-defined dose levels		
Steps	Dose Levels	Number of patients	
DL-1	IRI 150/REGO 80	0-6	
DL1	IRI 150/REGO 120	3-6	
DL2	IRI 180/REGO 120	3-6	
DL3	IRI 180/REGO 160	3-6	

The 6 patients treated at the RP2D in the phase I part will be included in the phase II part.

- **Phase I and II:**

**FOLFIRINOX** will be administered as per standard procedures: every 14 days (**1 cycle = 14 days**):

Oxaliplatin (Eloxatin® or generic drug): 85mg/m^2 on day 1, IV infusion over 2 hours, immediately followed by

- Folinic acid 400 mg/m^2 or Calcium Levofolinate: 200mg/m^2 given as a 2-hour IV infusion, with the addition, after 30 minutes of
- Irinotecan (Campto® or generic drug) : 150-180 mg/m^2 as per dose-level given as a 90-minute intravenous infusion through a Y-connector immediately followed by

5-Fluorouracil: 400mg/m^2 IV bolus then 2400mg/m^2 over 46 hours continuous infusion.

**Prophylactic G-CSF will be systematically given after each course from Day-7 to Day 12.**

**REGORAFENIB** will be given orally at a dose of 80 to 160 mg, as per dose-level, once daily on days 4 to 10 of each cycle

Tumor assessments (computed tomography (CT) or magnetic resonance imaging (MRI)) of the chest, abdomen, pelvis (if patient allergic to iodine contrast agents) will be performed at the baseline, every 8 weeks thereafter.

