	
considered. No study-related procedures will be performed that are not covered by the prescreening informed consent form.
 
Eligibility criteria for full study
 
Inclusion criteria
 
 
1. Written informed consent for full study.
 
2. Documentation of tumor RAS mutation, wild-type homozygous, heterozygous status of UGT1A1 gene. The status of UGT1A1 gene will be performed by the laboratory chosen by the investigator (for information, appendix 1).
 
3. Serum uracile < 16 ng/ml
 
4. Measurable disease, defined as at least one unidimensional measurable lesion on a CT scan, according to RECIST version 1.1.
 
5. ECOG performance status ≤1.
 
6. Life expectancy of at least 3 months.
 
7. Adequate bone marrow, renal and liver functions as evidenced by the following laboratory requirements within 7 days prior to study treatment initiation: 
 
a. Absolute neutrophil count (ANC) ≥ 1,500/ mm^3 without biologic response modifiers such as granulocyte colony-stimulating factor (G-CSF), within 21 days before the start of study treatment,
 
b. Platelet count ≥ 100 000/mm^3 , without platelet transfusion within 21 days before the start of study treatment,
 
c. Hemoglobin (Hb) ≥ 9 g/dL, without blood transfusion or erythropoietin, within 21 days before the start of study treatment,
 
d. Serum creatinine ≤ 1.5 x upper limit of normal(ULN)
 
e. Serum calcium ≥ LLN and ≤ 1.2 x UNL ; Serum magnesium ≥ LLN and ≤ 1.2 x UNL ; Kalemia ≥ LLN,
 
f. Glomerular filtration rate as assessed by the estimated glomerular filtration rate (eGFR) ≥ 50 mL/min per 1.73
 
 
 

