**Hematologic DLT:**

- Grade 4 (NCI-CTCAE V5) neutropenia lasting > 3 days,
- Febrile neutropenia Grade 3 (ANC < 1,000/mm^3 with fever ≥ 38.5 °C) (CTCAE V5),
- Febrile neutropenia Grade 4 (life-threatening consequences; urgent intervention indicated),
- Grade 4 (NCI-CTCAE V5) anemia (i.e life-threatening consequences; urgent intervention indicated),
- Platelets < 25 000 /mm^3 or platelets < 50 000 /mm^3 associated with bleeding,
- INR or PTT elevation of Grade ≥ 3 (NCI-CTCAE V5) with associated bleeding,
- Grade ≥ 3 hemorrhage/bleeding events (NCI-CTCAE V5).

**Phase II:** 48-week disease-control rate (defined as the rate of non-progressing patients after central review, at 48-week post-initiation of therapy, to all treated patients.

Treated patients who have progressed or died before the 48-week evaluation will be considered as failure.

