Including skin assessment for toxicities

Pre-menopausal women of childbearing potential only

12-lead ECG will be performed before and after the administration of Oxaliplatin during the three first cycles (Phase I and II) beyond cycle 3, ECG will be performed before administration of oxaliplatin

Includes: albumin, creatinine, creatinine clearance calculated according MDRD, lipase, glucose, TSH (every 6 weeks of CXD1), , total protein and uric acid

Liver function tests will be performed weekly during the three first cycles of treatment

Not required at day 1 of cycle 1 if those were completed within 7 days

Dipstick assessment with pH, protein, glucose, bilirubin, ketones, blood cells and leucocytes

CT scan of the abdomen, pelvis and chest or if the patient is allergic to iodine contrast agents, hepatic MRI and CT scan of the pelvis and chest without injection; RECIST criteria version 1.1

CT-Scans will be performed every 8 weeks

If the last radiological tumor assessment > 1 month

CT-Scan of safety follow-up will be performed if only it weren't done at the EOT visit

Period for DLT assessment is the three first cycles (only Phase I)

Height only at screening

Blood pressure will be monitored every other week during the first 3 cycles of treatment

Continuously from screening until FU visit, 30 days after last administration of study drug

A treatment diary will be handed over to patient on cycle 1 day 1

Three EDTA tubes will be collected at baseline, every 8 weeks during treatment and at the end of treatment

Paraffin-embedded human solid tissue blocks will be sent off at room temperature at the end of the enrollments

Only for unstabilized adverse events since the end of treatment

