## 5.2 Screening period

Enrollment into FOLFIRINOX-R will be performed in two stages with two separate informed consent forms. Initially, all potential patients will consent to undergo molecular testing.

Molecular testing :

Only patients with RAS mutated tumor status, wild-type homozygous status of DPD and wild-type homozygous, heterozygous status of UGT1A1 will be screened for the study treatment.

**Each centre will choose its DPD and UGT1A1 genotyping laboratory. For your information a list is provided by the sponsor (cf appendix 1). The sponsor will bear the cost of the genotyping analysis (we draw your attention to the analysis of phenotyping which will not be reimbursed by the sponsor).**

A second consent form to screen for the clinical study (Clinical Trial Consent).

Both consent processes are independent of each other.

The following procedures and assessments will be performed **around 21 days of starting study Drug :**

- Obtainment of two informed consents
- A blood sample will be collected then will be shipped to laboratory that you will have chosen. To determine the DPD and UGT1A1 status (cf appendix 1). Check with the laboratory for the number, type and volume of blood tubes
- Documentation of RAS mutation
- Eligibility criteria checked
- Physical examination including review of all organ systems, examination of pertinent organ systems).
- Radiological tumor assessment using the RECIST criteria, version 1.1 (see appendix 4) must be performed. (CT scan of the abdomen, pelvis and chest or hepatic MRI and CT scan of the pelvis and chest without injection).  
A PET scan is not acceptable for radiological evaluation
- All additional suspected sites of disease should be imaged. An appropriate radiological evaluation should be obtained if bone metastases are suspected (e.g., bone scan)
- 12-lead ECG
- Complete medical history including demographics, allergies, prior surgery and prior chemo/radiation therapy with documentation of treatment response. See section XX for detailed instructions on the differentiation between medical history and adverse events

The following procedures and assessments will be performed **within 7 days of starting study drug:**

- Eligibility criteria checked
- ECOG performance status (appendix 5)
- Adverse events
- Physical examination including review of all organ systems, examination of pertinent organ systems, weight, BSA and height.

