**The following assessments should be performed at each evaluation i.e (every 8 weeks):**

- Tumor markers CEA (Carcino-Embryogenic Antigen), CA 19.9 (Carbohydrate Antigen 19-9)
- Radiological tumor assessment using the RECIST criteria, version 1.1 (see appendix 4) must be performed. (CT scan of the abdomen, pelvis and chest or hepatic MRI and CT scan of the pelvis and chest without injection)
- Physical examination with weight, BSA

- Three 7-ml EDTA tubes for cfDNA (not supplied). After centrifugation, the plasma will be frozen at -80°C until shipment.

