## 7. Blinded independent central review (BICR)

A central review of CT-scans is planned for patients found progression-free at 48 weeks. They will be submitted to a independent panel of radiologists for review of tumor response.

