## 9.4. ASSESSMENT CRITERIA

Phase I: Identify the maximum-tolerated dose (MTD) of Folfirinox combination with regorafenib in Patients with metastatic colorectal cancer.

Phase II:

Non-progression rate (OR+SD): The tumor response will be assessed by the investigator using RECIST guidelines v1.1 (2009). The non-progression rate will be presented as a percentage with a 95% confidence interval.

Objective response (OR): The tumor response will be assessed by the investigator using RECIST v1.1 criteria, from the first course of chemotherapy, until disease progression. Patients with suggestive symptoms of disease progression should be evaluated at the time of onset of symptoms. An objective response is defined as a complete (CR) or a partial (PR) response.

The best objective response rate will be reviewed at the end of treatment and presented as a percentage with a confidence interval of 95%.

Survival:

Progression-free survival (PFS): Survival Delays will be calculated in months from the date of inclusion to the date of the considered event: First documented disease progression or death from any cause.

Living patients without disease progression will be censored at the last known date.

Rates and median PFS will be estimated using Kaplan-Meier method and presented with its 95% confidence interval.

Overall survival (OS): The overall survival time will be calculated in months from the date of inclusion to the date of death from any cause. Living patients will be censored at the last known date.

Rates and median overall survival will be estimated using the Kaplan-Meier product limit method and presented with its 95% confidence interval.

The median follow-up will be calculated using the "reverse Kaplan-Meier method".

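### The alternative imaging route (liver MRI plus unenhanced CT of chest and pelvis) does not require the abdomen outside the liver, which the synopsis does, and the sections disagree on who may use it

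*Combined protocol and SAP*

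**What the plan says.** **Coverage.** The synopsis, under treatment modalities, calls for "Tumor assessments (computed tomography (CT) or magnetic resonance imaging (MRI)) of the chest, abdomen, pelvis (if patient allergic to iodine contrast agents", at baseline and then every 8 weeks. Footnote 10 in section 5.1 keeps CT of abdomen, pelvis and chest as the standard and adds: "if the patient is allergic to iodine contrast agents, hepatic MRI and CT scan of the pelvis and chest without injection". Section 5.3, for the 8-weekly evaluation, has "CT scan of the abdomen, pelvis and chest or hepatic MRI and CT scan of the pelvis and chest without injection". Sections 5.2, 5.4 and 5.5 offer the same two options.

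**Access.** The synopsis and footnote 10 mention iodine allergy. The visit instructions in sections 5.2 to 5.5 do not.

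**Related provisions.**
- At screening, section 5.2 adds: "All additional suspected sites of disease should be imaged".
- On treatment, section 9.4 says: "Patients with suggestive symptoms of disease progression should be evaluated at the time of onset of symptoms". Section 5.3 schedules CEA, CA 19-9 and a physical examination every 8 weeks.
- The phase II endpoint (section 2.2.1) is the "48-week disease-control rate (defined as the rate of non-progressing patients after central review, at 48-week post-initiation of therapy, to all treated patients".
- Section 7 says: "A central review of CT-scans is planned for patients found progression-free at 48 weeks".
- Inclusion criterion 4 (synopsis and section 4.2) asks for: "Measurable disease, defined as at least one unidimensional measurable lesion on a CT scan".

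**The concern.** The standard option names the abdomen. The alternative puts the liver in its place, so nodes, peritoneum and retroperitoneum drop out of what must be imaged. The same protocol therefore demands two different levels of coverage, and a site working from section 5 alone would see no allergy condition on the lesser one.

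The endpoint is non-progression at 48 weeks in a single-arm trial. If a patient stays on the alternative route and progresses silently in the abdomen outside the liver, a failure can be recorded as a success, and no control arm shares the error. Central review reads scans that were taken; it cannot supply anatomy that was not acquired. Response rate and disease control rate are exposed in the same way. PFS is less exposed, because it also counts progression assessed clinically by the investigator.

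**Working it through.** **1. Provisions side by side**

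| Place | Abdominal coverage on the alternative route | Condition for using it |
|---|---|---|
| Synopsis, treatment modalities | whole abdomen | iodine allergy (in parentheses) |
| Section 5.1, footnote 10 | liver only | iodine allergy |
| Sections 5.2, 5.3, 5.4, 5.5 | liver only | none stated |

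The synopsis and the body differ on coverage. Footnote 10 and sections 5.2 to 5.5 differ on access.

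**2. Do other provisions close the gap?** The instruction on additional suspected sites stands under screening only. The section 9.4 evaluation depends on symptoms. Markers and examination every 8 weeks may prompt further imaging, but the plan does not say that they must. Each lowers the chance of a miss; none guarantees that a silent new abdominal lesion is imaged.

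**3. The plan's own design figures (section 10.1)**

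Inputs: p0 = 0.35, p1 = 0.50, alpha 5% (taken as one-sided; the plan does not say), power 80%, go if at least 29 of 65 succeed.

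n = [(1.645 × √(0.35 × 0.65) + 0.842 × √(0.50 × 0.50)) / 0.15]² = 64.57, rounded up to 65. With 5% non-evaluable, 65 / 0.95 = 68.4, rounded up to 69. Both stated figures reproduce.

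The exact binomial properties of the 29/65 rule are P(X ≥ 29 | p = 0.35) = 6.9% and P(X ≥ 29 | p = 0.50) = 83.9%. The 6.9% is the starting point for what follows and comes from the decision rule, not from imaging.

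**4. Size of the effect, on assumed inputs**

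Let f be the share of patients on the alternative route and m the share of true failures on that route that are missed. The documents give neither. Only true failures can become false successes, so at p0:

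- apparent rate = 0.35 + 0.65 × f × m
- expected false successes in 65 = 65 × 0.65 × f × m
- false-go probability = P(X ≥ 29 | n = 65, apparent rate)

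With m = 10%:

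| f | Apparent rate | False successes in 65 | False-go probability |
|---|---|---|---|
| 0 | 0.3500 | 0 | 6.9% |
| 3% (allergy only) | 0.3520 | 0.13 | 7.4% |
| 5% (allergy only) | 0.3533 | 0.21 | 7.7% |
| 20% (worst case) | 0.3630 | 0.85 | 10.4% |
| 30% (worst case) | 0.3695 | 1.27 | 12.5% |

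The result also moves with m. At f = 5%, m = 5% gives 7.3% and m = 30% gives 9.4%. The calculation assumes that each patient stays on one route throughout.

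**The case against.** **The wide-use reading is strained.** Both places that state a condition tie it to iodine allergy, and scanning without injection fits that purpose. The unconditional wording in sections 5.2 to 5.5 reads most naturally as a shortened restatement of footnote 10. On that reading the effect is well under one patient. This stands, and it is why 20-30% usage is shown only as a worst case.

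**The other safeguards matter.** Symptom-triggered evaluation, markers and examination will catch some of these progressions. This also stands, though silent lesions remain.

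**Stronger readings the documents do not support.** A reader might infer any of the following:
- *The rest of the abdomen is never imaged on this route.* No field of view or scan limits are given, and adjacent abdomen may be captured. What can be said is that it is not required.
- *The error can only raise the success count.* That holds only if the route stays constant. A patient with liver MRI at baseline and full abdominal CT later could have old extra-hepatic lesions read as new, which would lower the count.
- *Nothing requires the same route throughout.* The assessments refer to the RECIST criteria in appendix 4, whose content is not in the text available for this review, so its absence cannot be claimed.
- *An iodine-allergic patient with liver-only disease cannot meet criterion 4.* An earlier or additional CT could qualify, and the criterion does not demand contrast. The wording is merely out of step with the permitted modality.

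**Conclusion.** The inconsistency is real on two counts: abdominal coverage, and who may use the alternative route. Followed as written in section 5, the plan allows silent extra-hepatic abdominal progression to go unimaged and be counted as 48-week disease control in a patient kept on that route, with no later remedy.

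The likely size is small. If the route is confined to allergic patients (assumed 3-5%) and 10% of their true failures are missed, the false-go probability rises by 0.5 to 0.8 percentage points (7.4 − 6.9 and 7.7 − 6.9). The worst case adds 3.5 to 5.6 points, but it needs 20-30% usage, for which the documents offer no support. The usage and miss rates are assumptions throughout. Severity: minor. It is worth correcting because images not taken by week 48 cannot be recovered.

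**What to change.** Reconcile footnote 10 and sections 5.2 to 5.5 with the synopsis, so that one rule applies at baseline and at every assessment:

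1. Attach the iodine-allergy condition to the alternative route wherever it appears.
2. Make the route cover the whole abdomen, for example by extending the unenhanced CT already planned for chest and pelvis through the abdomen.
3. State that the route used at baseline is kept through week 48, unless appendix 4 already says so.
4. Reword criterion 4 in the synopsis and section 4.2 to accept a measurable lesion on CT or MRI.

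The cost is protocol wording and a somewhat longer acquisition in the few patients on this route. No extra visit is needed.
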